5. SAFETY MONITORING AND REPORTING

5.1 Definition of an Adverse Event

An adverse event (AE) is any untoward or unfavorable medical occurrence in a human participant that occurs within 48 hours of a study-related blood draw that is possibly, probably, or definitely related to the blood draw. Any event outside of this 48 hours window period will not be considered an AE for this study.

No adverse event to be considered since sputum collection is a non-invasive procedure.

5.2 Definition of an Serious Adverse Event

Serious adverse event is any adverse event that:

- results in death;
- is life-threatening (places the participant at immediate risk of death from the event as it occurred);
- results in inpatient hospitalization or prolongation of existing hospitalization;
- results in a persistent or significant incapacity;
- results in a congenital anomaly/birth defect; or based upon appropriate medical judgment, may jeopardize the participant's health and may require medical or surgical intervention to

prevent one of the other outcomes listed in this definition.

- results in death;
- is life-threatening (places the participant at immediate risk of death from the event as it occurred);
- results in inpatient hospitalization or prolongation of existing hospitalization;
- results in a persistent or significant incapacity;
- results in a congenital anomaly/birth defect; or based upon appropriate medical judgment, may jeopardize the participant's health and may require medical or surgical intervention to prevent one of the other outcomes listed in this definition.
- 5.3 Definition of an Unanticipated Problem

An unanticipated problem is defined as any incident, experience, or outcome that is defined as:

- 1. Unexpected in terms of nature, severity, or frequency in relation to:
 - the research risks that are described in the research protocol and informed consent document or other study documents; and
 - the characteristics of the participant population being studied; and
- 2. Related or possibly related to the participation in the research; and
- 3. Places participants or others at a greater risk of harm (including physical, psychological, economic, or social harm) than was previously known or recognized or is an SAE.

5.4 Reporting Procedures to the IRB

All unanticipated problems and SAEs, regardless of relationship, will be reported by the site PI to the IRB within 7 working days of the investigator's awareness.

All reportable adverse events (events that occur within 48 hours of the research blood draw and are possibly, probably, or definitely related to the research blood draw) will be reported in the summary form to the IRB at the time of Continuing Review.

5.5 Study Monitoring

The study will be conducted in compliance with this protocol, International Conference on Harmonization (ICH) Guidelines for Good Clinical Practice (GCP) and any applicable regulatory requirement(s). Independent monitors, under contract by the Sponsor, will visit the clinical research site to monitor all aspects of the study in accordance with the appropriate regulations. The objectives of a monitoring visit will be:

- 1. To verify the prompt reporting of all data points, including reporting SAEs, and also check the availability of a signed informed consent form (ICF).
- 2. To review the consistency of each participant's records with the source documents.
- 3. To ensure compliance with the protocol, and accuracy and completeness of records.

The monitors also will inspect the clinical site regulatory files to ensure that regulatory requirements are being followed. During the monitoring visits, the site investigator (or designee) and other study personnel will be available to discuss the study progress and monitoring visit.

The site investigator (or designee) will make study documents (e.g., ICFs and CRFs) and pertinent hospital or clinical records readily available for inspection by the local institutional review board/ethics committee (IRB/EC), the local and national regulatory authorities, and the site monitors for confirmation of the study data.

5.6 Safety Monitoring Plan

The investigators will monitor protocol data that could affect patient safety or confidentiality, including AEs, documentation of patient evaluation, treatment, and disposition, and coding of patient data and samples. Additionally, independent monitors will conduct visits based on a mutually agreed schedule to monitor study documents.

6. ETHICAL CONSIDERATIONS

6.1 Informed Consent Process

Informed consent is a process in which information is presented to enable persons to voluntarily decide whether to participate as a research participant. It is an ongoing conversation between the human research participant and the researchers covering the essential information about the study which begins before consent is given and continues until the end of the participant's involvement in the research.

All volunteers will sign an ICF after discussion of essential information about the research by the study staff. This will include the purpose of the study, duration, procedures, alternatives, risks, and benefits. Participants will have the opportunity to ask questions about the study and have their questions answered.

All participants in the study will sign/thumb print an appropriate informed consent document prior to any procedures being done specifically for the study. The participants may withdraw consent at any time throughout the course of the study. A copy of the informed consent document will be given to the participants for their records. The researcher will document the signing of the consent form in each participant's study record.

6.2 Illiterate Participant

If the volunteer is illiterate, oral consent will be obtained. The administrator of the oral consent will sign and date the form. The adult volunteers will thumbprint the consent form. An impartial witness should be present during the entire informed consent discussion and should sign and date the consent form.

6.3 Premature Withdrawal of Participant

Participants may voluntarily withdraw from the protocol at any point in the study. Attempts will be made to determine the reason that the subject wishes to withdraw.

6.4 IRB Review

Prior to the implementation of the protocol, the protocol and ICF for this study will be submitted for approval to the appropriate IRB. Any change to the protocol, ICF, will only be implemented after approval from the IRB. Records of the IRB review and approval of all the documents pertaining to the study will be kept on file by the site investigator and are subject to inspection at any time during the study. Continuing reviews or study progress report will be submitted according to the requirement of the appropriate IRB, but once a year at a minimum.

6.5 Participant Confidentiality

All records will be kept confidential to the extent provided by the law. The study monitors and other authorized representatives may inspect all documents and records required to be maintained by the site investigator, including, but not limited to, medical records. Records will be kept in a locked cabinet, and all computer entry and networking programs will be done with coded numbers only. Clinical information, attributable to the subject, will not be released without written permission of the subject, except as necessary for monitoring, the EC/IRB, or Office for Human Research Protections (OHRP).

The results of the research study may be published according to the INA-RESPOND policy, but subject names or identities will not be revealed.

6.6 Rationale for Subject Selection

Children and teenagers under age 18 are excluded from participating in the study due to concerns regarding long term study compliance.

6.7 Benefits

This study is meant to provide knowledge on the TB drug resistant in new and

previously treated TB cases in study hospitals and to identify areas of potential research in the future. It may not provide direct benefit to participants. Patients participating in this study will receive additional diagnostic and drug susceptibility testing not currently provided routinely.

The Site study team will share results with the study participants related to their medical care.

6.8 Compensation

This study will not provide any compensation for any visit schedules that are in accordance to national TB treatment guidelines. Patients who were diagnosed as DS-TB will receive Rp 150,000 as compensation at baseline visit, month 1, 2, end of treatment visit, and 6 months post treatment visit during study. Patients who were diagnosed as MDR-TB will receive Rp 150,000 as compensation at baseline visit, month 1, 2, 12, 18, end of treatment visit, and 6 months post treatment visit treatment visit during study. This compensation to compensate longer time taken and any inconveniences due to more study procedures.

6.9 Risk and Discomforts

This is a minimal-risk, observational study and does not involve experimental interventions. The only study intervention is a blood draw and all other procedures are considered as part of standard care for TB patients.

The hazards of blood drawing are minimal and consist of mild discomfort and or bleeding at the venipuncture site, bruising and rarely fainting and local infection. In case of any immediate serious side effect like fainting, the patient will be stabilized by the study team if needed.

The hazards of sputum collection are minimal and consist of mild discomfort when participants tried to produce sputum to be collected.

Each drug susceptible subject in this study will undergo one additional chest x-ray at the end of study. The purpose of this x-ray is to determine if the subject has improved chest x-ray. The amount of radiation the subject will receive is 0.040 rem (which is below the guideline of 5 rem per year allowed for research participants by the NIH Radiation Safety Committee). The hazard of an additional (maximum two with 6 months interval) chest x-ray are minimal and consist of mild discomfort and radiation exposure when participants undergo the chest x-ray process.

6.10 Recording/Documentation

At each contact with the subject, assessment information will be elicited by appropriate questioning and examination, and they will be recorded on source documents. Source documents may include worksheets, progress notes, laboratory reports, consult notes, and data collection tools. Data is to be transcribed onto CRFs from source documents on an ongoing basis during the study. The study monitor may review and audit all documents and records required to be maintained by the site investigator.

Any type of corrections to study documents should be initialed and dated by the person who is making the correction. The site investigator is responsible for ensuring that the data collected are complete, accurate, and recorded in a timely manner. All CRFs should be reviewed, initialed and dated by the site investigator or designee. CRFs will be maintained and kept in locked cabinets at the site for at least 5 years after study completion.

Each subject's name will be paired with a numeric code in the enrollment log. Access to data identifying participants will be kept in a locked file, accessible only by study staff. Finally, the importance of subject confidentiality will be impressed upon all research staff. The site investigator is responsible for the accuracy and completeness of the data reported.

7. PROTECTION OF INTELLECTUAL PROPERTY (IPR), MATERIAL TRANSFER AGREEMENT (MTA), AND GENETIC RESOURCES AND TRADITIONAL KNOWLEDGE (GRTK)

7.1 Protection of Intellectual Property

Publication of the results of this study will be governed by the INA-RESPOND publication policy. Any presentation, abstract, or manuscript will be made available for review by the supporters prior to submission.

7.2 Publication and Dissemination of Research Results

These will be guided by the Protection of Intellectual Property (IPR) terms as outlined in Article X and Annex I of the Science and Technology agreement between the Government of the Republic of Indonesia and the Government of the United States of America. Article X (Protection of Intellectual Property) states:

- Provisions for the protection and distribution of intellectual property created or furnished in the course of cooperative activities under this Agreement are set forth in Annex I, which shall form an integral part of this Agreement.
- 2. Scientific and technological information of a non-proprietary nature resulting from cooperation under this Agreement (other than information which is not disclosed for commercial or industrial reasons) shall be made available, unless otherwise agreed, to the world scientific community through customary channels and in accordance with normal procedures of the participating agencies and entities.

And under Paragraphs III.A and III.B(1), (2)(a), (2)(b), (2)(c) of Annex I, Intellectual Protection

Rights, of the Science and Technology agreement between the Government of the Republic of Indonesia and the Government of the United States of America.

7.3 Material Transfer Agreement

Research materials used in the collaborations under this protocol may, on agreement of the participants, be transferred using Material Transfer Agreements (MTAs) as appropriate in the particular collaborations, as outlines in Article VIII of the Science and Technology Agreement.

7.4 Genetic Resources and Traditional Knowledge

The collection, conservation and exchange of genetic resources and associated traditional knowledge under this protocol shall be subject to Article VI of the S and T Agreement and will be based on the following considerations:

Obtaining informed consent from appropriate authority/institutional review board prior to accessing genetic resources collected during the conduct of this protocol.

Equitably sharing the benefits arising from the use of traditional knowledge and genetic resources.

The complete Science and Technology agreement between the Government of the Republic of Indonesia and the Government of the United States of America is in Appendix C.

APPENDIX A. List of Study Procedures and Timeline

Procedures	BL	Mo1	Mo2	Mo3	Mo4	Mo5	Mo6	Mo7	Mo8	Mo9	Mo10	Mo12	Mo14	Mo16	Mo18	Mo20	Mo22	Mo24	6Mos Post Tx
Tiooodaloo								End of T	reatment							End of T	reatment	T	
Screening Log	ST ST																		
Enrollment Log	ST ST																		
Informed Consent	ST ST																		
Demography	SOC SOC																		
TB history & contact history	SOC SOC																		
Smoking Habit	ST ST																		
Treatment seeking	ST ST																		
HIV, DM, cancer comorbid data	ST,IA ST,IA	IA IA	IA IA	IA IA	IA IA	IA IA	IA IA	IA IA	IA IA	IA IA	IA IA	IA IA	IA IA	IA IA	IA IA	IA IA	IA IA	IA IA	
Symptoms	ST ST	ST ST	ST ST	ST ST	ST ST	ST ST	ST ST	ST ST	ST ST	ST ST	ST	ST ST							
Treatment Compliance		ST ST	ST ST	ST ST	ST ST	ST ST	ST ST	ST ST	ST ST	ST ST	ST								
Height	ST ST																		
Weight	SOC SOC	SOC SOC	SOC SOC	SOC SOC	SOC SOC	SOC SOC	SOC SOC		SOC SOC	SOC SOC	SOC	ST ST							
Chest X-Ray	SOC SOC						SOC	S				SOC			SOC			ST	ST ST
AFB	ST ST	ST IA	SOC IA	IA IA	IA	IA IA	IA	SC IA)C IA	IA	IA	IA	IA	IA	IA	IA	IA	IA	
Xpert MTB/RIF	ST SOC																		
Sputum Culture	ST ST	ST ST	ST ST	SOC	SOC	SOC	SOC	SOC		SOC	SOC	SOC	SOC	SOC	SOC	SOC	SOC	SOC	
1 st DST	ST SOC																		
2 nd DST	ST ST																		

INA 102

Version 5.0

10/02/2017

																	- 1	02,201	
Procedures	BL	Mo1	Mo2	Mo3	Mo4	Mo5	Mo6	Mo7	Mo8	Mo9	Mo10	Mo12	Mo14	Mo16	Mo18	Mo20	Mo22	Mo24	6Mos Post Tx
Procedures								End of T	reatment							End of T	reatment		Post IX
Hb, HbA1C,	ST																		
HIV exams	ST																		
Ureum, Creatinin,	IA																		
AST, ALT	SOC																		
Stored Whole	ST																		
Blood (DNA)	ST																		
Stored Plasma	ST	ST	ST					S	T										
	ST	ST	ST													S	Ţ		
Stored PBMC	ST	ST	ST					S	T										
	ST	ST	ST													S	Ţ		
Stored Serum	ST																		
	ST																		
Stored Paxgene	ST	ST	ST					S											
	ST	ST	ST													S	Ţ	1	
Stored Urine	ST	ST	ST					S											
	ST	ST	ST													S	Ţ		
Stored Sputum	ST	ST	ST					S	T										ļ
-	ST	ST	ST													S	Ţ		ļ
Stored Mtb	ST	ST	ST					S	T										
Isolate	ST	ST	ST													S	Ţ	1	ļ
Stored Saliva	ST							S	T										
Stored Sunta	ST															S	T		

*ST for HIV and DM, If available for other comorbidities

Blue	: Information for DS-TB
Red	: Information for MDR-TB
ST	: Procedure required by study that might be different from the site SoC
SoC	: Procedure must be done regularly on site

IA : Procedure might be done on site for all or some groups of participants

All available data must be recorded for study

Variables	Measurement	Operational definition
New TB cases	Patient report	TB patients who never have TB treatment or already have TB treatment less than one month (4 weeks)
Previously treated TB cases	Patient report	A patient who has been treated for one month or more with anti TB drugs in the past
Presumptive TB	Clinical and X-Ray evaluation	Patient who presents with symptoms or signs suggestive of TB on the basis of X-ray suggestive TB
Bacteriologically confirmed TB	Laboratory evaluation	A participant whom a biological specimen is positive by AFB or culture or WRD (such as Xpert MTB/RIF)
Clinically diagnosed TB	Clinical and X-Ray evaluation	Participant who does not fulfil the criteria for bacteriological confirmation but has been diagnosed with active TB by a clinician or other medical practitioner who has decided to give the patient a full course of TB treatment, includes cases diagnosed on the basis of X-ray abnormalities
Pulmonary TB	Clinician judgement	Any bacteriologically confirmed or clinically TB involving the lung parenchyma or the tracheobronchial tree, including miliary TB, patient with both pulmonary and extrapulmonary TB should be classified as a case of PTB.
Extrapulmonary TB	Clinician judgement	Any bacteriologically confirmed or clinically diagnosed case of TB involving organs other than the lungs, e.g. pleura, lymph nodes, abdomen, genitourinary tract, skin, joints
Drug Sensitive/susceptible TB	By the result of Drug susceptibility test (DST)	Negative DST result
MDR TB	By the result of Drug susceptibility test (DST)	DST result positive resistant to isoniazid and rifampicin
Rif Resistance TB	By the result of Drug susceptibility test (DST)	DST result positive resistant to rifampicin

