4.4 Population and Sample Size

This is a descriptive study with the goal of estimating rates MDR in two separate cohorts (new and previously treated TB cases). WHO global report in 2013 estimated 1.9% MDR TB cases in new TB cases and 12% MDR TB cases in previously treated TB cases for Indonesia. This study will analyze 250 bacteriologically confirmed new TB participants and 250 bacteriologically confirmed previously treated participants. We estimate that 25% of presumptive new TB participants who satisfy study entry criteria will be bacteriologically confirmed TB. Similarly, we estimate that 70% of previously treated cases will be bacteriologically confirmed TB. Therefore, to obtain 500 bacteriologically confirmed TB cases and 357 presumptive previously treated cases will be enrolled, for a total of 1,357 enrolled. The proportion of confirmed TB cases amongst new and previously treated cases is an estimation and will be re-evaluated during the course of the study. Refer to the interim analysis section below for details.

Table 4.4.1 describes the expected precision (confidence bounds and width) for observed proportion of MDR amongst previously treated cases. With 250 participants and an observed MDR proportion of 12%, the confidence interval will be (0.085, 0.162). The precision of the estimated proportion of MDR does not improve considerably when increasing the sample size to 300. The confidence interval for a sample size of 300 with an MDR proportion of 12% is (0.085, 0.162), while decreasing the sample size to 200 has a more striking impact on the bounds increasing the lower bound to 0.078 and the upper bound to 0.173.

When considering the sample size for new TB cases, we note that the precision of binomial confidence intervals based on exact Clopper Pearson method increases as the proportion gets closer to zero. As a result, we find the true MDR rate is more precisely estimated with a sample size of 250 for new TB cases (compared to previously treated cases, where the MDR rate is expected to be around 12%). With a sample size of 250

new TB cases, the expected 95% confidence interval is (0.007, 0.046). (Table 4.4.1) Exact Clopper Pearson binomial confidence interval method formula:

$$\left(1 + \frac{n - x + 1}{xF\left[1 - \frac{1}{2}\alpha; 2x, 2(n - x + 1)\right]}\right)^{-1} < \theta < \left(1 + \frac{n - x}{[x + 1]F\left[\frac{\alpha}{2}; 2(x + 1), 2(n - x)\right]}\right)^{-1}$$

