4.5 Inclusion and Exclusion Criteria

The following inclusion and exclusion criteria are used when determining eligibility patients into the study:

- 4.5.1 Inclusion Criteria
 - Patients suspected of having pulmonary TB
 - Cough ≥ 2 weeks
 - At least one other TB clinical symptom
 - Fever
 - Unexplained weight loss
 - Loss of appetite
 - Hemoptysis
 - Shortness of breath
 - Chest pain
 - Night sweats
 - Fatigue
 - Suggestive TB on chest x-ray based on pulmonologist or internist consultant of pulmonology opinion
 - Age \geq 18 years' old
 - Willing to be treated or evaluated at study site
 - Willing to have specimens stored for use in future studies
 - Patient denies having TB treatment for more than 7 days in the last 1 month (30 days).
- 4.5.2 Exclusion Criteria

Pregnancy or any serious condition includes, but not limited to, liver disease, chronic kidney disease, and psychiatric illness that might interfere with study compliance (based on the clinician judgment). In order to assess participant's pregnancy status, the attending clinician will ask the participant's first day of last menstrual period. The

final decision about participant's pregnancy status will be up to the attending clinician..

- 4.5.3 End of study criteria
 - Study completion (six months after end of treatment or six months after month 24th visit).
 - Participant desires to leave study or withdraw consent.
 - No sputum specimen for the examinations of AFB, Gene Xpert, and culture at baseline and enrollment visit.
 - No longer treated as TB patients.
 - Treatment interruption of two months or greater.
 - Death
 - Transfer to other health facility where follow up/evaluation is no longer possible.
 - Based on investigator's discretion it is in the participant's best interest to be discontinued from the study.
 - Participants who cannot be reached to complete the 6 months' post treatment by phone or direct visit.
 - Termination of study

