4.7.2 Analysis

This is an observational study to describe rates of MDR TB amongst new and previously treated TB cases in Indonesia. Risk factors for MDR will be evaluated as a secondary objective. Additional secondary objectives include a description of treatment outcomes (cure, failure, death, completed treatment) and evaluation of associated risk factors for poor outcome, comparison of diagnostic accuracy of AFB and Xpert MTB/RIF (relative to culture) and an estimation of Xpert MTB/RIF Rif susceptibility testing sensitivity and specificity relative to standard DST. Research objectives will be analyzed as described below.

Primary objective

 To estimate the rate of MDR-TB amongst new and retreated TB cases. Proportions of MDR will be estimated, along with exact 95% confidence intervals based on a binomial distribution. Case definitions of MDR, new and previously treated TB are provided in Appendix B.

Secondary objective

- To estimate treatment outcomes (cured, failed, died, treatment completion, and lost to follow up) according to susceptibility pattern. Proportions of participants within each category will be estimated along with confidence intervals. Definitions of treatment outcomes are provided in appendix B.
- 2) To evaluate risk/protective factors for treatment success (cured or completed treatment vs failed or died or loss to follow up). These factors include: demographics (age, sex), TB contact history, smoking habit, treatment seeking behavior, co-morbidities (HIV, DM), primary drug resistance, symptoms, no cavity in the lung, nutritional status, treatment regimens, compliance, numbers of bacteria and TB strains (e.g., Beijing). Logistic regression models will be used to describe associations of treatment success with these factors.
- 3) To evaluate risk/protective factors for treatment interruption (loss to follow up vs other treatment outcome). These factors include: demographics (age, sex), TB contact history, smoking habit, treatment seeking behavior, co-morbidities (HIV, DM, and other comorbidities), primary drug resistance, symptoms, cavity in the lung, nutritional status, treatment regimens, compliance, numbers of bacteria and TB strains (e.g., Beijing). Logistic regression models will be used to evaluate associations of treatment interruption with these risk factors.
- To compare clinically defined TB against laboratory confirmed TB. Accuracy will be estimated along with 97.5% confidence intervals.

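### Both primary MDR proportions rest on a new or previously treated class set by patient report alone; undisclosed earlier treatment could raise the new-case figure, by an amount that depends on an unknown misreport share.

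*Combined protocol and SAP*

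**What the plan says.** Appendix B defines a new case as "TB patients who never have TB treatment or already have TB treatment less than one month (4 weeks" and a previously treated case as "A patient who has been treated for one month or more with anti TB drugs in the past". The measurement entered for each is "Patient report", and nothing else. Other rows of the same appendix name further sources: source documents for the treatment regimen, a blister count as an alternative for compliance, and laboratory evaluation for bacteriological confirmation.

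Section 4.7.2 ties the primary analysis to these rows: "Case definitions of MDR, new and previously treated TB are provided in Appendix B". The analysis itself is "Proportions of MDR will be estimated, along with exact 95% confidence intervals based on a binomial distribution", with no sensitivity analysis for misclassification.

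Section 4.4 supplies the planning figures. For new cases: "We estimate that 25% of presumptive new TB participants who satisfy study entry criteria will be bacteriologically confirmed TB". For the other cohort: "we estimate that 70% of previously treated cases will be bacteriologically confirmed TB". Planned MDR is 1.9% in new and 12% in previously treated cases, with 250 confirmed cases analysed in each cohort.

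An inclusion criterion in 4.5.1 also relies on the participant's own statement ("Patient denies having TB treatment for more than 7 days in the last 1 month (30 days"). It concerns recent treatment and eligibility, and assigns nobody to a cohort.

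**The concern.** The class that separates the two primary estimates is never checked against anything. If a participant says there was no earlier treatment but a hospital or TB programme record shows a course of one month or more, the plan has no rule that moves that participant out of the new cohort.

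Two of the plan's own contrasts would make such an error count for more than its frequency suggests. Previously treated presumptive cases are expected to be confirmed far more often than new ones, so undisclosed cases would be over-represented once the new cohort is restricted to confirmed TB. Their expected MDR proportion is also about six times higher. Both push the new-case estimate upward, from a small base.

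The new-case proportion is one of two primary results, and the Background and the Policy Benefits section say the data are meant to inform the national programme. The exact binomial interval reflects sampling error only, so it would give no sign of this bias.

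**Working it through.** **Inputs from section 4.4.** Confirmation yield 25% (new) and 70% (previously treated); MDR 1.9% and 12%; n = 250 confirmed per cohort.

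**Assumptions (not in the documents).** m is the share of presumptive participants recorded as new who were in fact treated before for one month or more. Undisclosed cases are given the 70% yield and 12% MDR of declared ones. Nobody is misreported in the other direction.

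**The plan's own figures first.** Enrolment: 250/0.25 = 1,000 and 250/0.70 = 357.1, matching the stated 1,000 and 357. Precision: the exact Clopper-Pearson interval for 5 of 250 (2%) is (0.0065, 0.0461), matching the stated (0.007, 0.046).

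**Ratios.** Yield 0.70/0.25 = 2.8. MDR 0.12/0.019 = 6.3.

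**Formulas.** The undisclosed share among confirmed cases recorded as new is s = 0.70m / [0.70m + 0.25(1 − m)]. The apparent new-case MDR is q = 0.019 + s(0.12 − 0.019).

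Worked for m = 5%: s = 0.035/(0.035 + 0.2375) = 0.035/0.2725 = 12.8%; q = 0.019 + 0.1284 × 0.101 = 3.20%.

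**Coverage.** With n = 250, the exact 95% interval contains 1.9% when 1 to 9 MDR cases are observed (at 10 cases the lower bound is 0.0193; at 0 cases the upper bound is 0.0146). Coverage is therefore the binomial probability of 1 to 9 cases at rate q.

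| m | s | q | q / 1.9% | MDR cases expected in 250 | Coverage of 1.9% |
|---|---|---|---|---|---|
| 0 | 0 | 1.90% | 1.00 | 4.75 | 97% |
| 1% | 2.8% | 2.18% | 1.15 | 5.4 | 95% |
| 2% | 5.4% | 2.45% | 1.29 | 6.1 | 91% |
| 5% | 12.8% | 3.20% | 1.68 | 8.0 | 72% |
| 10% | 23.7% | 4.30% | 2.26 | 10.7 | 37% |

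**How much comes from the yield difference.** With equal yields, s = m, and m = 5% gives 0.019 + 0.05 × 0.101 = 2.4%. The unequal yields account for the rest of the rise to 3.2%.

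**Sensitivity at m = 5%.**
- MDR of 6% among undisclosed cases: 0.019 + 0.1284 × 0.041 = 2.4%.
- MDR of 16% among undisclosed cases: 0.019 + 0.1284 × 0.141 = 3.7%.
- The Background's later rates (2.9% and 16%) in place of 1.9% and 12%: 0.029 + 0.1284 × 0.131 = 4.6% against a true 2.9%.

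**The case against.** The best reply is that the size rests on inputs the plan does not contain. No section gives a rate of undisclosed treatment. Nothing shows that undisclosed cases share the yield or MDR of declared ones. Nothing rules out the opposite error, in which a new case is reported as previously treated. All of this stands, and it is why the result is given as a range under stated assumptions.

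A reader might infer that a handful of undisclosed cases is enough to distort the new-case result. The figures do not support that. At 1–2% (10 to 20 of 1,000 enrolled) the estimate moves by 0.3 to 0.5 percentage points, at most about 1.4 extra MDR cases in 250, well inside the planned interval.

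The 2.8 ratio concerns confirmation by AFB, culture or Xpert. MDR is defined by DST, which follows a positive culture, and no culture-specific yields are given. The concentration among DST-tested cases may therefore differ. This also stands.

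It can be said that records already have a place: TB history is a standard-of-care baseline item in Appendix A, available data must be recorded, and monitors compare participant records with source documents. None of these lets a record determine the class. The MOP and the more specific analysis plans mentioned in 4.7.2 might add a check, but they are not among the documents, and Appendix B is what the primary analysis cites.

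Finally, a class that depends on which records can be found would vary across ten hospitals, so it is debatable as the only primary class. That is accepted, and it shapes the fix.

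**Conclusion.** The point holds as a conditional one. Patient report is the sole basis of the class, and documented earlier treatment does not alter it. If undisclosed retreatment cases resemble declared ones, the new-case MDR proportion is biased upward: from 1.9% to about 2.2% at a 1% misreport share, 2.4% at 2%, 3.2% at 5% and 4.3% at 10%. That is minor against the planned precision at 1–2% and material from about 5%.

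The documents do not support saying that the estimate will be inflated, or that misreporting runs only one way. The size depends on the unknown share, on the yield and MDR assumed for undisclosed cases, and on the mix among DST-tested cases. Under the same model the previously treated proportion mainly loses cases; it is not biased if non-disclosure is unrelated to resistance. This is a worthwhile, inexpensive improvement and not a flaw that invalidates the design.

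**What to change.** **Appendix B.** For both cohort rows, change the measurement to patient report checked against the site medical record and the TB treatment record where available. Add one CRF field for the source of the treatment history.

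**Section 4.7.2.** Report the new and previously treated MDR proportions with exact 95% intervals twice: by patient report, and by the record-checked class, in which documented treatment of one month or more counts as previously treated. State in advance which is the headline. Give the number reclassified and the number for whom no record was found.

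**Cost.** Some extra record review at the sites, one CRF field and one additional table. No treatment or visit changes. Records will be incomplete and will vary by site, and treatment taken at primary health centres may not appear in hospital files. The check will therefore find only part of the error, and a low reclassification count must be read beside the number with no record.
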